**Protocol Schemas for Arm 1B and Arm 2B**  
**Nivolumab plus dorgenmeltucel-L - Arm 1B**  
**Nivolumab Alone – Arm 2B**

Arm 1B: HAM + NIVOLUMAB			
Month	Week	Day	Treatment
	1	1	HAM
	2	8	HAM
	3	15	HAM
1	4	22	HAM + NIVO
	5	29	REST
	6	36	HAM + NIVO
	7	43	REST
2	8	50	HAM + NIVO
	9	57	REST
	10	64	HAM + NIVO
	11	71	REST
3	12	78	HAM + NIVO
	13	85	REST
	14	92	HAM + NIVO
	Evaluate for Response		
	15	99	REST
4	16	106	HAM + NIVO
	17	113	REST
	18	120	HAM + NIVO
	19	127	REST
5	20	134	HAM + NIVO
	21	141	REST
	22	148	HAM + NIVO
	23	155	REST
6	24		HAM + NIVO
	Evaluate for Response		
	Continue Nivolumab Q2 weeks		
7			HAM
8			HAM
9			HAM
	Evaluate for Response		
10			HAM
11			HAM
12			HAM
	Evaluate for Response		
15			HAM
	Evaluate for Response		
18			HAM
	Evaluate for Response		
21			HAM
	Evaluate for Response		
24			HAM
	Evaluate for Response		

Arm 2B: NIVOLUMAB ALONE		
Week	Day	Treatment
1	1	NIVO
2	8	REST
3	15	NIVO
4	22	REST
5	29	NIVO
6	36	REST
7	43	NIVO
8	50	REST
9	57	NIVO
10	64	REST
11	71	NIVO
12	78	REST
	Evaluate for Response	

Nivolumab Alone Group: Continue treatment Q2 weeks until disease progression or significant toxicity. Evaluate disease every 3 months. If disease progresses, subjects go off study but will continue to be followed for survival status.

**Protocol Schemas for Arm 1C and Arm 2C**  
**Pembrolizumab plus dorgenmeltucel-L - Arm 1C**  
**Pembrolizumab Alone – Arm 2C**

Arm 1C: HAM + PEMBROLIZUMAB			
Month	Week	Day	Treatment
	1	1	HAM
	2	8	HAM
	3	15	HAM
1	4	22	HAM + Pembro
	5	29	REST
	6	36	HAM
	7	43	Pembro
2	8	50	HAM
	9	57	REST
	10	64	HAM + Pembro
	11	71	REST
3	12	78	HAM
	13	85	Pembro
	14	92	HAM
	Evaluate for Response		
	15	99	REST
4	16	106	HAM + Pembro
	17	113	REST
	18	120	HAM
	19	127	Pembro
5	20	134	HAM
	21	141	REST
	22	148	HAM + Pembro
	23	155	REST
6	24		HAM
	Evaluate for Response		
	Continue Pembrolizumab Q3 weeks		
	7		HAM
	8		HAM
	9		HAM
	Evaluate for Response		
	10		HAM
	11		HAM
	12		HAM
	Evaluate for Response		
	15		HAM
	Evaluate for Response		
	18		HAM
	Evaluate for Response		
	21		HAM
	Evaluate for Response		
	24		HAM
	Evaluate for Response		

Arm 2C: PEMBROLIZUMAB ALONE		
Week	Day	Treatment
1	1	Pembro
2	8	REST
3	15	REST
4	22	Pembro
5	29	REST
6	36	REST
7	43	Pembro
8	50	REST
9	57	REST
10	64	Pembro
11	71	REST
12	78	REST
	Evaluate for Response	

Pembrolizumab Alone Group: Continue treatment until disease progression or significant toxicity. Evaluate disease every 3 months. If disease progresses, subjects go off study but will continue to be followed for survival status.

**PRECIS**

According to statistics of the American Cancer Society, an estimated 73,800 individuals will be diagnosed with melanoma and 9,900 will die of the disease in 2015 in the United States despite current therapy. This protocol attempts to exploit an approach to melanoma immunotherapy using a naturally occurring barrier to xenotransplantation in humans to increase the effectiveness of immunizing patients against their melanoma. The expression of the murine  $\alpha(1,3)$ galactosyltransferase [ $\alpha(1,3)$ GT] gene results in the cell surface expression of  $\alpha(1,3)$ galactosyl-epitopes ( $\alpha$ gal) on membrane glycoproteins and glycolipids. These epitopes are the major target of the hyperacute rejection response that occurs when organs are transplanted from non-primate donor species into man. Human hosts often have pre-existing anti- $\alpha$ -gal antibodies that bind  $\alpha$ -gal epitopes and lead to rapid activation of complement and cell lysis. The pre-existing anti- $\alpha$ -gal antibodies found in most individuals are thought to be due to exposure to  $\alpha$ -gal epitopes that are naturally expressed on normal gut flora leading to chronic immunological stimulation. These antibodies may comprise up to 1% of serum IgG.

In this phase 2b study, patients with advanced Stage melanoma will receive immune checkpoint inhibition consisting of ipilimumab, nivolumab, or pembrolizumab per the treating physician's standard of care. In addition to the immune checkpoint therapy, half of the patients will also receive dorgenmeltucel-L. Dorgenmeltucel-L is composed of irradiated allogeneic melanoma cell lines (HAM-1, HAM-2 and HAM-3). These cell lines have been transduced with a recombinant Moloney murine leukemia virus (MoMLV)-based retroviral vector expressing the murine  $\alpha(1,3)$ GT gene. Endpoints of the study include safety assessments, efficacy, and immunological responses.

## 1 INTRODUCTION

### 1.1 Objectives

#### 1.1.1 Primary Objective:

To assess safety of an anti-tumor treatment using immune checkpoint inhibition consisting of ipilimumab, nivolumab, or pembrolizumab alone compared to immune checkpoint inhibition plus dorgenmeltucel-L immunotherapy in Stage IV melanoma patients and to assess efficacy as indicated by progression-free survival of those patients treated with immune checkpoint inhibition with or without dorgenmeltucel-L immunotherapy.

#### 1.1.2 Secondary Objectives:

To assess the overall response rate, duration of response, duration of stable disease, and overall survival (OS) of patients with Stage IV melanoma treated with immune checkpoint inhibition with or without dorgenmeltucel-L immunotherapy.

To assess the immunological response of patients with metastatic melanoma undergoing anti-tumor treatment using immune checkpoint inhibition with or without dorgenmeltucel-L immunotherapy in Stage IV melanoma patients.

## 2 BACKGROUND

### 2.1 *$\alpha(1,3)$ Galactosyltransferase gene therapy and the hyperacute rejection response.*

#### *Hyperacute rejection of non-human xenografts*

Strong pre-existing immunological barriers to xenotransplantation of solid organs from lower mammals into humans can destroy a transplanted organ within minutes to hours, a phenomenon termed hyperacute rejection.[1] It has been demonstrated that the major cause of hyperacute rejection induced with porcine xenografts transplanted into baboons is secondary to expression of the enzyme  $\alpha(1,3)$ galactosyltransferase [ $\alpha(1,3)$ GT] and the resulting presentation of  $\alpha$ gal residues on the transplanted pig organs.[1,2]  $\alpha(1,3)$ GT is expressed in all mammalian species including the mouse (*Mus musculus*), but it is not present in old world primates, apes or humans.[3] The  $\alpha(1,3)$ GT gene is not active in humans due to the presence of two base pair frame shift mutations resulting a non-functional pseudogene.[4] Alpha(1,3)GT normally catalyzes the transfer of galactose from uridine-diphosphate galactose (UDP-Gal) to the N-acetyl-lactosamine acceptors on carbohydrate side chains in a specific  $\alpha(1,3)$ linkage on a large number of glycoproteins or glycolipids (Gal $\beta$ 1 $\rightarrow$ 4GlcNAc-R).

Anti- $\alpha$ gal antibodies present in human sera can recognize this epitope.[3] In fact, pre-existing human antibody against  $\alpha$ gal represents almost 1% of total human antibody. These  $\alpha$ gal epitopes are the targets for complement-mediated hyperacute rejection.[5] Our strategy will attempt to use

murine  $\alpha(1,3)$ GT as a therapeutic transgene in combination with an allogeneic cellular immunotherapy to induce hyperacute rejection of human melanoma.

***Other potentially important effects on the immune system***

Previous studies have established that multiple membrane glycoproteins on pig cells present  $\alpha$ gal residues and are targets for human anti- $\alpha$ gal antibody binding [6]. In addition, many glycoproteins possess multiple carbohydrate side chains and can express multiple different  $\alpha$ gal epitopes. Since both opsonization and complement fixation are dependent on epitope density,  $\alpha(1,3)$ GT immunogene therapy offers potential advantages over other candidate transgenes. The  $\alpha(1,3)$ GT gene expression could permit a large number of membrane glycoproteins to be induced to express these epitopes simultaneously. Opsonization of tumor cells can occur by pre-existing or induced anti- $\alpha$ gal antibodies and should significantly enhance tumor antigen presentation to macrophages by  $\alpha$ gal-antibody complex binding to their Fc-receptors. Studies demonstrated that the uptake of human tumor cells into macrophages are significantly enhanced by cell membrane modifications with enzymes using a recombinant, truncated form of an  $\alpha(1,3)$ GT.[7] These results using enzymatic modifications of human cell membranes should be transferable to our gene transfer approach. Previous attempts of immunotherapy have employed single cytokine molecules (e.g., IL-2, IL-12, GM-CSF) or single rejection antigens (e.g., HLA B7, melanoma specific tumor antigens) while the  $\alpha(1,3)$ GT approach offers the possibility of a broad xenogenization of normal antigens found on tumors.

***In humans, implanted murine retroviral vector producer cells (VPC's) are another type of  $\alpha$ gal-positive xenograft***

VPC's have been used for *in vivo* gene delivery as a potential improvement over direct administration of vector alone to increase transduction efficiency in both animal models and human clinical trials.[8-10] It has been demonstrated that murine retroviral VPC's and the viral vectors they produce both express  $\alpha$ gal-residues and therefore are efficiently lysed by antibody and complement within 30 minutes after being exposed to human serum. This is due to the expression of  $\alpha$ gal-residues on the cells and the viral envelope derived from the VPC membrane.[11] Link and coworkers demonstrated that heparin, enoxaparin, or sCR1 (soluble form of Complement receptor 1) can specifically block lysis of murine cells by human serum.[12] These workers hypothesized that this disadvantage for murine VPC's could be an advantageous novel method to destroy tumor cells. The hypothesis is that expression of the  $\alpha(1,3)$ GT gene using a retroviral vector in allogeneic melanoma cancer cells will lead to  $\alpha$ gal epitope expression and anti- $\alpha$ gal antibodies that are known to be present and in high titer in the majority of patients should then bind this epitope and activate the classical and alternative pathway of complement to induce tumor cell lysis possibly enhancing tumor immunogenicity.

## 2.2 Pre-Clinical Experience of Dorgenmeltucel-L

All of the components of dorgenmeltucel-L immunotherapy have been evaluated in a variety of preclinical studies in mice as well as in phase 1 and 2 human clinical studies. The safety of dorgenmeltucel-L has been demonstrated *in vivo* in mice. Substantial preclinical data on the safety and efficacy of related immunotherapies have been published. Specific preclinical information is available in the Investigator's Brochure.

## 2.3 Clinical Experience of Dorgenmeltucel-L (HyperAcute Melanoma)

In the phase 1 dorgenmeltucel-L Trial NLG0104, 6 subjects received the melanoma immunotherapy. Six patients, 2 men and 4 women, mean age- 60 years (range, 36-76), were vaccinated with one priming dose of 500 million cells and up to eleven booster doses of

300 million cells. Observed events unrelated or unlikely to be related to the immunotherapy included Grade 1 fatigue, pruritus, nausea, vomiting, constipation, dysphagia, dermal change, facial edema, hyperglycemia, pain, and nocturia. Grade 1 events possibly related to the immunotherapy included fatigue, nausea, and dysgeusia. Grade 2 events unrelated or unlikely related to the immunotherapy include pruritus, cellulitis, left hemianopsia, and headache. One Grade 3 cellulitis was observed after a brown recluse spider bite in one of the subjects. Events probably or definitely related to the immunotherapy include Grade 1 and 2 injection site reactions to include redness, swelling, and itching. Five of the six patients went off study, 3 due to progression of disease and 2 due to concurrent illness. One subject remains on long-term follow-up with stable disease (> 5 years).

Riker *et al.* have since completed a phase 2 clinical trial of dorgenmeltucel-L (NLG12036, NewLink Genetics) combined with pegylated interferon (Sylatron™, Merck). Trial design consisted of a 12-week regimen with the initial 4 weekly treatments consisting of dorgenmeltucel-L alone (intradermally) followed by 8 additional treatments of dorgenmeltucel-L plus Sylatron™ (subcutaneously, 6 µg/kg). Trial endpoints include clinical response, overall safety and correlative findings for observed anti-tumor effect. They report a total of 25 patients accrued with a median age 60, 68% male with 21 patients completing the trial, 4 stopped due to progressive disease (PD).

By RECIST criteria, of 16 Stage IV patients, there were 2 complete responders (CR), 1 with stable disease (SD) and 4 with no evidence of disease (NED) after resection. For Stage III patients, 4/9 remains NED, 1 patient with slowly progressive disease with a single site resected and currently NED. The median overall survival is 29 months, with 60% of the patients surviving for >1 year and 12/25 (48%) still alive. All evaluable patients (21/21) seroconverted, developing autoimmune antibodies. Vitiligo developed in 4/25 patients, correlating with 2 CR and 2 NED.

They conclude that combinatorial immunotherapy with dorgenmeltucel-L plus Sylatron™ shows clinical efficacy with tumor regression and concomitant immune activation. Optimization of dosing schedules and therapeutic efficacy should be further explored in order to enhance the benefit of this promising immunotherapeutic approach (Riker *et al.*, *The Ochsner Journal*, 14 (2) 2014:164-174).

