## 5 **DOSING INFORMATION**

The study is designed to evaluate the addition of dorgenmeltucel-L to standard of care checkpoint immunotherapy. The following information about ipilimumab, nivolumab, and pembrolizumab is provided as background and drawn from the package inserts of the respective immunotherapies. The information should not be considered complete nor comprehensive. The administration of

these agents (ipilimumab, nivolumab, and pembrolizumab) should be done at the direction of the treating physician according to the physician's usual standard of care practices.

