### **Specific Risk/Adverse Events with ipilimumab**

Ipilimumab can result in severe and fatal immune-mediated adverse reactions due to T-cell activation and proliferation. These immune-mediated reactions may involve any organ system; however, the most common severe immune-mediated adverse reactions are enterocolitis, hepatitis, dermatitis (including toxic epidermal necrolysis), neuropathy, and endocrinopathy. The majority of these immune-mediated reactions initially manifested during treatment; however, a minority occurred weeks to months after discontinuation of ipilimumab.

Permanently discontinue ipilimumab and initiate systemic high-dose corticosteroid therapy for severe immune-mediate reactions. Assess patients for signs and symptoms of enterocolitis, dermatitis, neuropathy, and endocrinopathy and evaluate clinical chemistries including liver function tests and thyroid function tests at baseline and before each dose. For specific details of toxicity management, the treating physician is instructed to refer to the package insert for ipilimumab and to follow the instructions and algorithms therein.

Specific attention to development of autoimmune events during periodic study visits can be evaluated by an optional checklist provided in **Appendix E**. This checklist in addition to the serologic tests obtained can be used by the study physicians to determine if further evaluation for autoimmune disease is warranted by an appropriate specialist in the organ system affected. This can be done to avoid misinterpretation of spurious autoimmune test results.

Trials using immunomodulatory agents such as ipilimumab CTLA-4 have shown a correlation between disease response and so called autoimmune breakthrough events (ABEs) like hypophysitis, colitis, autoimmune hepatitis, or dermatitis. It is for this reason that they are distinguished from other adverse events.

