### ***11.3 Evaluation of Benefits and Risks***

The benefits of this immunization approach are theoretical and it is hoped that the induction of an acute rejection response to the  $\alpha(1,3)$ galactosylated residues on the allogenic melanoma cancer cells used to immunize the patient will lead to cross-recognition of weak native tumor antigens on the patient's melanoma cells that may be shared with the genetically engineered immunotherapy cells. By generating an antibody and cellular immune response against the patient's tumor, it is hoped that the patient may benefit by a tumor response.

Given the safety demonstrated with transfer of murine retroviral vector producer cells in several studies that naturally express the  $\alpha(1,3)$ GT enzyme and have 1,3- $\alpha$ -galactosylated residues, and the poor prognosis of this patient population, it is believed that the possible benefits from tumor response and improved survival probability far outweigh the risk to the patient. The information obtained in this study may be extremely valuable in the treatment of melanoma and other malignancies in the future. The patients to be entered in this protocol have refractory or recurrent melanoma and limited life expectancies. The chance of this experimental treatment to provide clinical benefit is unknown. All possible benefits and known risks will be carefully explained to all patients and an Informed Consent Document will be signed by the patient prior to entrance into the protocol.

There are no anticipated serious adverse side effects to the immunization technique employed in this study. Theoretical risks may include the induction of unanticipated autoimmune disease and/or liver, kidney, lung, heart and CNS damage and/or coagulopathy and bleeding as a result of excessive activation of the complement (C') system. Expected risks and discomforts to the patients are minimal and will be those of needle sticks and phlebotomy. An acceptable adverse event profile was developed in the Phase I part of the trial. Patients will be observed for one hour after each immunization for allergic/hypersensitivity reactions. Patients will be treated as deemed medically appropriate for any immediate or delayed adverse event related to the immunization.

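### Section 11.3 understates risks that the protocol itself reports, and the only visible checklist for clinical autoimmune events is optional and appears only in the ipilimumab text

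*Combined protocol and SAP*

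**What the plan says.** **Risk statement.** Section 11.3 (Evaluation of Benefits and Risks) states: "Expected risks and discomforts to the patients are minimal and will be those of needle sticks and phlebotomy". It continues: "Theoretical risks may include the induction of unanticipated autoimmune disease", among other organ effects.

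**Reported experience.** Section 2.3 describes a phase 1 trial of six subjects. Grade 1 and 2 injection-site reactions were judged probably or definitely related to the vaccine; fatigue, nausea and dysgeusia were judged possibly related. It then describes a 25-patient phase 2 trial in which the vaccine was "combined with pegylated interferon (Sylatron™, Merck"). The findings there were: "All evaluable patients (21/21) seroconverted, developing autoimmune antibodies. Vitiligo developed in 4/25 patients, correlating with 2 CR and 2 NED". Section 5.1 says that most recipients of HyperAcute products have a rapid local inflammatory reaction and that some have a delayed one. It names injection-site reactions, fatigue and nausea as the most frequent related events in the melanoma trials.

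**How autoimmune events are sought.** Section 5.2, in the text on ipilimumab risks, says: "Specific attention to development of autoimmune events during periodic study visits can be evaluated by an optional checklist provided in" Appendix E. Section 5 introduces the checkpoint-inhibitor information by saying that it "is provided as background and drawn from the package inserts of the respective immunotherapies". The matching risk texts for nivolumab (5.3) and pembrolizumab (5.4) mention no checklist.

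**Setting.** Section 1.1.1 makes safety of the combination against checkpoint inhibition alone a primary objective. Section 12.2 makes the trial open-label.

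**The concern.** There are two separate issues.

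First, Section 11.3 is where an ethics committee looks for the balance of risk and benefit. It confines expected discomforts to those of needles and blood sampling, and treats autoimmunity as hypothetical. Other sections of the same protocol report common vaccine-related reactions, and autoimmune findings under a vaccine-containing regimen.

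Second, the trial adds the vaccine to drugs whose main harms are immune-mediated, and then compares the arms on safety. Symptomatic autoimmune events in skin, bowel, joints or nerves are found largely by asking and examining. If a structured search is optional, investigators know the allocation, and one arm is seen more often, a difference in search could appear as a difference in toxicity. If the checklist is hardly used, mild events may be missed in both arms.

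**Working it through.** **1. Section 11.3 against the rest of the protocol**

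| Topic | Section 11.3 | Elsewhere |
|---|---|---|
| Expected discomfort | Only that of needles and blood sampling | 2.3: Grade 1–2 injection-site reactions, probably or definitely related. 5.1: acute local reaction in most recipients; fatigue and nausea also frequent |
| Autoimmunity | Theoretical | 2.3: autoantibodies in 21/21 and vitiligo in 4/25, with interferon co-treatment |

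The first row does not depend on the interferon trial, since no co-treatment is described for the six phase 1 subjects. The second row is weaker. Autoantibodies are a laboratory finding, and vitiligo is the clinical event.

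**2. What the counts can carry (exact 95% intervals)**

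- Autoantibodies: 21/21 = 100%; lower limit 0.025^(1/21) = 83.9%.
- Vitiligo: 4/25 = 16.0%; interval 4.5% to 36.1%.
- Autoimmune events listed in phase 1: 0/6; upper limit 1 − 0.025^(1/6) = 45.9%.

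The phase 2 trial gave four weekly treatments of vaccine alone and then eight with interferon, and no comparator is described. The counts show what was seen under the combination, not what the vaccine caused. Six subjects with no listed event do not exclude an effect either.

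**3. Visits early in treatment (schemas and Section 8 calendars)**

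| Pair | Arm 1, treatment visits to Week 14 | Arm 2, dosing visits to Week 13 |
|---|---|---|
| A (ipilimumab) | Weeks 1, 2, 3, 4, 6, 7, 8, 10, 12, 13, 14 = 11 | Weeks 1, 4, 7, 10 = 4, plus a Week 13 assessment |
| B (nivolumab) | Weeks 1, 2, 3, 4, 6, 8, 10, 12, 14 = 9 | Weeks 1, 3, 5, 7, 9, 11, 13 = 7 |
| C (pembrolizumab) | Weeks 1, 2, 3, 4, 6, 7, 8, 10, 12, 13, 14 = 11 | Weeks 1, 4, 7, 10, 13 = 5 |

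Contact is greater in Arm 1 in every pair. Pair A is the extreme and pair B is close. The calendar for Arm 1B is not in the text available, so its visits come from the schema.

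**4. Can the bias be sized?** If the true event rate p is equal in both arms, the checklist raises detection by g, and the share of patients in whom it is used differs by Δu, then

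false difference = p × g × Δu.

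The documents give none of these three inputs. Assuming g = 0.90 − 0.60 = 0.30:

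- equal use (Δu = 0): 0 points at any p;
- p = 0.30, use 80% against 40%: 0.30 × 0.30 × 0.40 = 3.6 points, or 0.036 × 50 = 1.8 patients per arm;
- p = 0.40, use in all against none: 0.40 × 0.30 × 1 = 12 points.

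In the middle case the observed rates are 0.30 × (0.9 × 0.8 + 0.6 × 0.2) = 25.2% and 0.30 × (0.9 × 0.4 + 0.6 × 0.6) = 21.6%. The standard error of their difference with 50 per arm is √(0.252 × 0.748/50 + 0.216 × 0.784/50) = 8.5 points. A range from 0 to 12 points that rests wholly on assumed inputs is not an estimate.

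**5. Would checkpoint-inhibitor visits serve as time points?** Counting those visits to Week 13 gives 4 in Arm 1A (Weeks 4, 7, 10, 13) and 4 in Arm 2A (Weeks 1, 4, 7, 10); 5 in 1B and 7 in 2B; 4 in 1C and 5 in 2C. Arm 1 starts the checkpoint inhibitor at Week 4, so the counts differ in two pairs and the timing differs in all three. A schedule counted from Day 1 is needed.

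**The case against.** The strongest reply is that safety capture does not rest on the checklist. Section 10.6 requires all adverse events, whatever their grade or attribution, to be recorded on study and for 30 days after the last dose. The available calendars schedule liver chemistry and thyroid tests in both arms. Section 12.3 plans laboratory shift tables by CTCAE grade. Sections 4.6 and 10.6 name autoimmune disorders in the long-term gene-transfer follow-up. All of this stands. A reader might infer that the whole safety comparison is left to unblinded discretion, and the documents do not support that. What remains is narrower: the recording rule covers events that are observed and does not say how symptomatic ones are to be sought.

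The checklist may also not be the only tool. Section 5.2 says that it is used alongside serologic tests, and several calendar rows and Section 7 are redacted. It would be wrong to infer that no autoimmune testing is planned. The statement here is limited to the unredacted text and to clinical events. That Appendix E is missing from the contents list shows little, because Appendices C and D are cited and unlisted too.

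Placement in the ipilimumab text does not by itself favour an arm, because randomization is stratified by checkpoint inhibitor and both Arms 1A and 2A fall under that text. Heavier use of the checklist in vaccinated patients is plausible but not shown.

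On Section 11.3, its wording concerns autoimmune disease, not antibodies, and an ethics committee that reads the whole protocol will find the reactions in Sections 2.3 and 5.1. That limits the harm but does not make the sections agree.

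**Conclusion.** The point holds in two limited parts.

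- Section 11.3 is inconsistent with Sections 2.3 and 5.1. The conflict over local reactions, fatigue and nausea is direct. The conflict over autoimmunity is one of disclosure: autoantibodies in 21/21 and vitiligo in 4/25 (16%, 4.5% to 36.1%) were observed under vaccine plus interferon. A reader might conclude that the vaccine causes autoimmunity. An uncontrolled combination trial cannot show that.
- No required, arm-neutral method for finding symptomatic autoimmune events is visible, in an open-label trial with comparative safety as a primary objective and unequal visits (11 against 4 in pair A, 9 against 7 in B, 11 against 5 in C). Detection depends partly on unblinded judgement. Neither the size nor the existence of a resulting bias can be established from the documents.

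This rests on the unredacted text and on calendar tables that may have been damaged in extraction. The change is worth making because it is cheap and serves a primary objective, not because a large bias has been shown.

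**What to change.** 1. **Section 11.3.** Reconcile the statements on expected and theoretical risks with Sections 2.3 and 5.1. Cite the injection-site reactions, fatigue and nausea, and the autoantibody and vitiligo counts, noting the interferon co-treatment and the absence of a described comparator.

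2. **Checklist.** Make the Appendix E checklist required in all six arms, include it in the protocol, and add it to every study calendar. Use the same number of matched time points within each arm pair, counted from randomization or Day 1 and not from checkpoint-inhibitor doses:
   - baseline;
   - Weeks 1, 4, 7, 10 and 13 in pairs A and C, all of which are existing visits;
   - the nearest scheduled visits in pair B, all within one week of those targets: Arm 1B at Weeks 1, 4, 6 or 8, 10, and 12 or 14; Arm 2B at Weeks 1, 3 or 5, 7, 9 or 11, and 13;
   - each 3-monthly imaging visit thereafter.

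**Cost.** Protocol wording, one more form, and a few extra minutes at visits that already take place. The time is an assumption, since the content of Appendix E is not in the text available. The additional vaccine visits in Arm 1 remain, so the change reduces unequal detection but does not remove it.
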